10.5.4.4. Additional Efficacy Analyses

Thrombin generation parameters (with ETP as the primary measure) will be obtained at baseline, 1 hour, and 12 hours post-randomization. The difference between the two treatment groups will be evaluated using a mixed effects model similar to the model described below for the analysis of the NIHSS and GCS scores.

The change from baseline in NIHSS and change from baseline in GCS will be analyzed using a mixed linear model with covariates, including the baseline measurement and the following fixed effect terms:

- Stratification factor of time from symptom onset to baseline imaging scan (< 180 minutes vs. ≥ 180 minutes)
- Treatment arm (usual care/andexanet)
- Time (measurements at 2, 3, 6, 12, 24, and 72 hours post-randomization)
- Treatment-by-time interaction

Patients will be treated as a random effect to take account of the correlation of the measurements within the same patient.

Neurologic deterioration at 24 hours defines deterioration as meeting at least one of the following 2 criteria:

- An increase in NIHSS score ≥ 4 at 24 hours post-randomization compared with baseline;
- A decrease in GCS score ≥ 2 at 24 hours post-randomization compared with baseline.

The CMH test stratified by time from symptom onset to baseline imaging scan will be used to test the treatment difference in the proportion of neurologic deterioration at 24 hours.

Change from baseline in mRS scores at 30 days post-randomization will be analyzed using a proportional odds model adjusted for baseline mRS, the stratification factor, treatment arm, and potentially other clinical factors.

The relationship between anti-fXa activity and the achievement of clinical events such as hemostatic efficacy and mortality will be evaluated. A logistic regression adjusted for potentially other clinical factors, the stratification factor in the primary efficacy analysis, and treatment arm will be used to evaluate the relationship.

Further details of these analyses will be provided in the SAP.

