5.5.3. Modified Rankin Scale

The modified Rankin Scale (mRS) score will be obtained at baseline (premorbid) and at 30 days post-randomization or at the Early Termination Visit. If the baseline mRS is unavailable during Screening, the mRS can be collected from the participant, relative, caregiver, or legally authorized representative at a post-randomization time point as long as the mRS reflects the participant's premorbid (ie, pre-ICrH) neurologic status. The premorbid mRS should reflect the

participant's neurologic status prior to acute illness. Tabulation of mRS scores at baseline and Day 30 will be provided by treatment group.

mRS at 30 days post-randomization will be dichotomized into 1 (functional independence: scores of 0, 1, 2, and 3) and 0 (functional dependence: scores of 4 and 5; death: score of 6). A logistic regression model will be used to analyze mRS at Day 30, adjusting for baseline mRS, time from symptom onset to the baseline imaging scan, and treatment group. The odds ratio for the treatment effect with 95% CI will be reported.

Summaries of shifts in functional independence from baseline to Day 30 will also be provided by treatment group.

By-participant listings of mRS will be provided.

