5.5.8. European Quality of Life 5-Dimension 5-Level

Health-related quality of life assessed by the European Quality of Life 5-Dimension (EQ-5D) questionnaire at 30 days post-randomization is collected either on the participant or through a medical proxy. For analyses, data for both participant and proxy will be pooled. The pooled data will be summarized by treatment group by European Quality of Life 5-Dimension 5-Level (EQ-5D-5L). Comparison between andexanet and UC will be performed for each dimension in terms of "no problems" (Level 1) and "any problems" (Levels 2, 3, 4, and 5), using a CMH test adjusting time from symptom onset to the baseline imaging scan.

Statistical Analysis Plan ALXN2070 18-513 (Amendment 3)

The EQ-5D-5L index value and visual analog scale will be summarized as continuous variables. The difference between treatment groups will be evaluated using an ANCOVA adjusted for time from symptom onset to baseline imaging scan. The LS mean difference between the 2 treatment groups and its 95% CI will be presented.

By-participant listings of EQ-5D-5L data will be provided.

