5.7.2.5. Deaths

The number and percentage of participants with AEs leading to death will be presented by SOC and PT as described above.

All deaths will be assessed by the EAC blinded to treatment group. Deaths occurring up to 30 days post-randomization will be referred below as 30-day death or 30-day mortality. Bleeding mortality is defined as deaths occurring within 72 hours post-randomization not associated with TEs.

All 30-day deaths, 30-day death occurring during index hospitalization, and bleeding-related mortality (defined as any death within 72 hours from randomization and not associated to the occurrence of an identified TE) will be summarized by treatment group and total based on the following causes:

- All causes
- Cardiovascular (CV) causes (resulting from myocardial infarction, sudden cardiac death, heart failure, stroke, cerebral vascular procedures, CV hemorrhage, or other)
- Non-CV causes (resulting from non-CV hemorrhage and non-CV procedure or surgery)

Time to death by all causes up to 30 days post-randomization will be analyzed using a Cox proportional hazards model adjusted for time from symptom onset to the baseline imaging scan (< 180 minutes versus \geq 180 minutes) and treatment group. Participants who did not die or discontinued prior to Day 30 will be censored at the day of the last assessment.

Page 28 of 52 Alexion Confidential Kaplan-Meier method will be used to analyze time to death with the same censoring rule. Participants who completed the study (ie, Day 30) will be censored at the day of the last assessment. Probabilities of 30-day death at different time points and median time to death will be presented by treatment group.

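### The SAP's 30-day mRS, mortality and EQ-5D models adjust for neither index-bleed severity nor age, which costs precision in supportive comparisons

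*SAP*

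**What the plan says.** SAP Section 5.5.3 dichotomizes Day-30 mRS (0-3 versus 4-6) and states: "A logistic regression model will be used to analyze mRS at Day 30, adjusting for baseline mRS", together with the onset-to-scan stratum (below versus at or above 180 minutes) and treatment. The same section says that baseline mRS should reflect "neurologic status prior to acute illness".

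SAP Section 5.7.2.5 says that time to all-cause death "will be analyzed using a Cox proportional hazards model adjusted for time from symptom onset to the baseline imaging scan" and treatment group; nothing else is listed.

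SAP Section 5.5.8, on the EQ-5D index and visual analog scale: "The difference between treatment groups will be evaluated using an ANCOVA adjusted for time from symptom onset to baseline imaging scan".

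The protocol was more open. Its mRS analysis (Section 10.5.4.4) is a "proportional odds model adjusted for baseline mRS, the stratification factor, treatment arm, and potentially other clinical factors". Its mortality section (10.6.3) likewise leaves room for other clinical factors. Both leave the details to the SAP, which names no such factor. The SAP's binary logistic model also differs in form from the protocol's proportional odds model, and SAP Appendix 5 does not list that change.

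Severity data are planned. Baseline NIHSS and GCS are scheduled for all patients (Protocol 9.1.1, 9.1.4, Appendix A), as is the baseline scan, and the core laboratory measures hematoma volume (Protocol 3.1). The ICH score and baseline volume are subgroup factors for the primary endpoint (SAP 5.8). The SAP already adjusts the NIHSS and GCS models through 72 hours for the baseline score (SAP 5.5.4).

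**The concern.** Premorbid mRS describes the patient before the bleed and cannot stand in for how bad the bleed is. The eligibility range is wide: volume 0.5 to 60 mL, NIHSS up to 35, GCS 7 or more. Randomization is stratified only by intended usual-care agent and onset-to-scan time, so balance in severity and age is left to chance.

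When a strong baseline predictor is left out, chance imbalance in it stays in the treatment estimate, and the treatment test has less power than an adjusted one. These 30-day comparisons are the ones a reader will consult to see whether better hemostasis at 12 hours carries through to function, survival and quality of life. If the covariates are chosen only after unblinding, the adjusted results will be post hoc.

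**Working it through.** **The plan's own power figure.** The only one is for the primary endpoint: about 90% for 70% versus 80% with 450 per group (Protocol 10.3). With a pooled null standard error of √(2 × 0.75 × 0.25 / 450) = 0.02887, an alternative standard error of √((0.21 + 0.16) / 450) = 0.02867 and the final level 0.0277 (z = 2.201), power = Φ[(0.10 − 2.201 × 0.02887) / 0.02867] = Φ(1.27) = 89.8%. With the two looks at 0.0310 and 0.0277 it is 91.2% with no dropout and 88.0% with an assumed 10%. The statement reproduces, but it says nothing about the 30-day models, for which no power, effect size or prognostic strength is given.

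**Assumed inputs.** mRS 0-3 in 40% versus 50%, or 40% versus 47%. Death by Day 30 in 30% versus 22% (the protocol introduction puts 30-day mortality above 30-40%). One standard-normal severity covariate of varying strength, expressed as its AUC for the outcome. Two-sided 0.05. N = 900, or 450 for the efficacy endpoints if the trial stops at the interim.

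**Method.** Logistic: logit P = a + θ·treatment + γ·severity + 0.4·premorbid, with θ set so that the arm-level percentages stay fixed as γ rises. The model was fitted with and without severity, premorbid status being in both (1,000 runs). Cox: exponential times censored at Day 30, with and without severity (600 runs). The onset-to-scan stratum was left out of all models. The effective-sample ratio is (mean z adjusted / mean z unadjusted)².

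| Model, total N, assumed rates | AUC | Power without → with | Gain (points) | Effective-sample ratio |
|---|---|---|---|---|
| mRS, 900, 40 v 50% | 0.63 | 85.2 → 88.8 | 3.6 | 1.05 |
| | 0.73 | 86.0 → 91.0 | 5.0 | 1.17 |
| | 0.81 | 86.7 → 94.3 | 7.6 | 1.41 |
| | 0.86 | 86.3 → 97.7 | 11.4 | 1.61 |
| mRS, 900, 40 v 47% | 0.63 | 59.3 → 60.1 | 0.8 | 1.05 |
| | 0.73 | 58.5 → 65.4 | 6.9 | 1.17 |
| | 0.81 | 57.5 → 72.6 | 15.1 | 1.43 |
| | 0.86 | 55.2 → 77.5 | 22.3 | 1.63 |
| mRS, 450, 40 v 50% | 0.63 | 57.0 → 58.6 | 1.6 | 1.04 |
| | 0.73 | 61.3 → 67.2 | 5.9 | 1.20 |
| | 0.81 | 59.4 → 72.5 | 13.1 | 1.38 |
| | 0.86 | 56.7 → 77.8 | 21.1 | 1.60 |
| Death, 900, 30 v 22% | 0.63 | 78.7 → 79.5 | 0.8 | 1.05 |
| | 0.74 | 80.8 → 87.5 | 6.7 | 1.23 |
| | 0.82 | 80.2 → 92.8 | 12.6 | 1.54 |

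A single simulated power has a Monte Carlo standard error of up to √(0.25 / 1000) = 1.6 points (2.0 for Cox). The smallest gains are therefore better read from the effective-sample ratio.

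**EQ-5D ANCOVA.** Power = Φ[d·√(n/2) / √(1 − R²) − 1.96], with n per arm and R² the variance explained by the added covariates. For an assumed d = 0.20 and n = 450: 85.1% at R² = 0 (0.20 × 15 = 3.0; Φ(1.04)), then 88.5, 91.8, 94.8 and 97.2% at R² = 0.1, 0.2, 0.3 and 0.4. For n = 225: 56.4%, then 60.9, 66.0, 71.8 and 78.2%.

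**Validity.** In a separate null simulation of the logistic model, type I error stayed near 5% with and without severity.

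**The case against.** **Size.** A reader might infer that these analyses lose substantial power. The documents do not support that, because they state neither prognostic strength nor a target effect for these endpoints. With weak severity the gain is only 1 to 4 points. This stands; only a range can be given.

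**Scope.** A reader might also infer that severity enters no SAP model, or that these are the trial's only functional comparisons. Neither is so. The 72-hour NIHSS and GCS models adjust for the baseline score and are listed under neurologic function. The point concerns 30-day outcomes only.

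**Missing baselines.** The measures are scheduled for everyone, not guaranteed. SAP Section 6.1 expects missing or out-of-window baseline NIHSS and scans, and sedated or intubated patients, while Section 5.5 rules out imputation for the additional efficacy endpoints. If patients with missing covariates were dropped, a 5% effective-sample gain would be cancelled by about 5% missing (1 − 1/1.05), and a 17-21% gain by about 15-17%. This stands, and the fix must include a rule.

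**Meaning of the estimate.** Less-adjusted odds and hazard ratios are not biased; they answer a different question. With rates held at 40% and 50% the marginal odds ratio is 1.50, while the conditional one in the simulation runs from 1.56 to 1.96 as severity strengthens. This stands: adjustment changes the target, and the SAP must say so.

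**Protocol wording.** The protocol said only that other factors might be used and named none, so it would be wrong to say that the SAP removed prespecified covariates. It left the option unused.

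**Stakes.** mRS and EQ-5D are additional endpoints and mortality is a safety endpoint; none is in the hierarchy of SAP Section 5.1.1. After an early stop, safety analyses use the larger second cutoff (SAP 1.2, 5.7), so the N = 450 figures do not carry over to mortality.

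**Conclusion.** The omission is real in all three SAP models. It is a loss of efficiency in supportive 30-day comparisons, with no consequence for type I error, the primary endpoint or the confirmatory conclusion.

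For mRS and mortality the power forgone is about 1 to 4 points at an AUC of about 0.63, 5 to 7 at about 0.73, and 8 to 22 at 0.81 to 0.86, or roughly 5% to 63% of effective sample size. For EQ-5D at d = 0.20 with 450 per arm it is about 3 to 12 points for R² from 0.1 to 0.4. The direction follows from the models as written; the size rests entirely on the assumed effects and prognostic strengths, and on complete covariate data. The change is worth making because it is cheap and because these outcomes will be used to interpret the hemostasis result.

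**What to change.** - In the Day-30 mRS logistic model and the 30-day mortality Cox model, prespecify baseline NIHSS (or GCS), log baseline hematoma volume and age as continuous covariates. In the EQ-5D ANCOVA, add the same plus premorbid mRS.
- For missing covariates, first apply the existing fallback for baseline values (SAP 6.1) and the rule for untestable GCS verbal scores (SAP 6.3.1). Then singly impute what remains from baseline data pooled across arms, so that no patient is dropped. State that this fills covariates, not outcomes, and is an exception to the no-imputation sentence in SAP 5.5.
- State that the adjusted odds and hazard ratios are conditional effects, and keep the current models as supportive analyses.
- While editing, record in SAP Appendix 5 the move from proportional odds to binary logistic for mRS.

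The cost is SAP wording and minor programming, with no new data. The one real trade-off is a conditional rather than a less-adjusted effect measure, which retaining the current models makes visible.

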5.5.4. NIHSS and GCS Through 72 Hours Post-randomization

Values of NIHSS and GCS at each visit and change and percent change from baseline at 2, 3, 6, 12, 24, and 72 hours post-randomization will be summarized by treatment group.

For both NIHSS and GCS, the difference between the 2 treatment groups in NIHSS and GCS change from baseline will be evaluated using MMRM separately, adjusting baseline scores. The LS mean difference in change from baseline and its 95% CI will be reported for each post-randomization visit, as well across all post-randomization time points through 72 hours.

The MMRM model that analyzes NIHSS and GCS will contain the following fixed-effect terms:

- Time from symptom onset to the baseline imaging scan (< 180 minutes versus ≥ 180 minutes)
- Treatment group (and examet versus UC)
- Visit (baseline, 2, 3, 6, 12, 24, and 72 hours post-randomization)
- Treatment-by-visit interaction

Participants will be treated as a random effect to take account of the correlation of the measurements within the same participant. An unstructured covariance matrix will be used to model within-participant variances. This model imposes no assumptions on mean trend and correlation structure and is considered robust. Denominator degrees of freedom will be estimated using the Kenward-Roger approximation. If there is a convergence problem due to the unstructured covariance matrix, the unstructured covariance matrix will be replaced by other covariance matrices in the following order until convergence is met: AR(1), Toeplitz, and compound symmetry.

By-participant listings of NIHSS and GCS data will be provided.

5.5.5. Effective Hemostasis With CT or MRI Scan

Effective hemostasis using only imaging parameters will be evaluated. The imaging parameter refers to change in hematoma volume between baseline and 12 hours by CT or MRI scan. An increase $\leq 35\%$ is considered excellent/good whereas a change > 35% is considered as poor/none. A CMH test stratified by time from symptom onset to the baseline imaging scan (< 180 minutes versus \geq 180 minutes) will be used. The difference in the proportion of

participants with effective hemostasis using only imaging parameters and its 95% CI will be estimated.

By-participant listings of effective hemostasis with CT or MRI Scan will be provided.

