10.5. Efficacy Endpoints and Analyses

10.5.1. Population

The primary, secondary, and additional efficacy endpoints will be analyzed using the ITT population.

10.5.2. Definitions

Hemostatic efficacy will be determined by the blinded EAC. Cases will be primarily determined to have effective hemostasis (i.e., a rating of "good" or "excellent") or not (i.e., a rating of "poor/none") based on pre-specified criteria documented in the Adjudication Charter and summarized in Appendix B.

For biomarker endpoints, the baseline measurement will be the most recent value drawn within 120 minutes prior to randomization. Any baseline measurement collected greater than 120 minutes prior to randomization will be considered out of window.

10.5.3. Efficacy Endpoints

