10.5.3.3. Additional Efficacy Endpoints

The additional efficacy endpoints include the following:

- Change from baseline in thrombin generation parameters (with ETP as the primary measure) obtained at 1 and 12 hours post-randomization.
- Proportion of neurologic deterioration, as defined by NIHSS increase ≥ 4 or a GCS score decrease ≥ 2 at 24 hours post-randomization versus baseline.
- Change from baseline in mRS score at 30 days post-randomization.
- Change from baseline in NIHSS score obtained at 2, 3, 6, 12, 24, and 72 hours post-randomization.
- Change from baseline GCS score obtained at 2, 3, 6, 12, 24, and 72 hours post-randomization.
- Proportion of patients with a ≥ 7-point increase from baseline in NIHSS at 12 hours post-randomization.
- Hemostatic efficacy evaluated using only imaging parameters.
- Proportion of patients receiving rescue therapy between 3 and 12 hours post-randomization.
- Correlation analysis between anti-fXa activity and the achievement of hemostatic efficacy.
- Health-related quality of life as assessed by the EQ-5D questionnaire at 30 days post-randomization.
- UW-mRS score at 30 days post-randomization.

10.5.4. Statistical Methodology for Efficacy Endpoint Analyses

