	• These cases will be further adjudicated to determine if they are non-evaluable from administrative reasons (e.g., scan not available for technical reason, transfer to another facility, or hematoma drainage not due to clinical deterioration) or clinical reasons (scan not available because of patient deterioration). Cases assessed as non-evaluable for clinical reasons will be imputed as having poor/none hemostatic efficacy.

Note: This Appendix is intended only as a guide to Investigators and is not intended to be comprehensive. Full details on the rating of hemostatic efficacy are provided in the Adjudication Charter.

^a Rescue therapies defined as any pro-coagulant replacement factor products (e.g., 3- and 4-factor prothrombin complex concentrates, activated PCCs, FEIBA[®], recombinant fVIIa, plasma, FFP, whole blood), any systemic or local hemostatic therapies (except tranexamic acid), or the conduct of unplanned surgeries/procedures to treat the hematoma.

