5. STATISTICAL ANALYSIS

5.1. General Considerations

During the conduct of the study, the Sponsor and Investigators will be blinded to the aggregated efficacy and safety summaries. In addition, all unblinded analyses that are required to support the DSMB will be performed by an independent unblinded DSMB statistician. These analyses will be performed under the direction of the DSMB according to the analyses described the DSMB Charter. The results of these unblinded analyses will not be available to the Sponsor or Investigators until after database lock.

The safety interim analyses will follow the same procedures as the efficacy interim analysis (see Protocol Section 10.7), with the Sponsor remaining blinded to the results of these analyses unless the DSMB recommends stopping the study early.

Once the study is complete and the final database lock is performed, the study will be fully unblinded and the final analyses will be performed.

All efficacy and safety endpoint parameters will be summarized descriptively.

For continuous variables, the number of observations, mean, median, SD, first quartile, third quartile, interquartile range, and minimum and maximum values will be presented. For categorical variables, unless specified otherwise, counts and percentages will be based on the number of participants with nonmissing values in each treatment group and total. Inferential statistics will be presented only when specified.

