5.5. Additional Endpoint Analysis

The tertiary efficacy endpoints are listed in Section 1.1. All tertiary efficacy analyses will be performed on the ITT Set. No missing data will be imputed.

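### The imaging-only hemostasis analysis has no rule for scans missing for clinical reasons, so as written it drops those ITT patients, with a bias that can go either way

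*SAP*

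**What the plan says.** Protocol 10.5.3.3 lists among eleven additional efficacy endpoints "Hemostatic efficacy evaluated using only imaging parameters". SAP 5.5.5 defines it: "The imaging parameter refers to change in hematoma volume between baseline and 12 hours by CT or MRI scan". Growth of at most 35% is excellent/good and anything larger is poor/none. The arms are compared by a CMH test stratified by time from symptom onset to baseline scan. The section has no category for a patient without a scan.

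Three general statements apply. SAP 5.5: "All tertiary efficacy analyses will be performed on the ITT Set. No missing data will be imputed". SAP 5.1, for categorical variables unless otherwise specified: "counts and percentages will be based on the number of participants with nonmissing values in each treatment group and total". Protocol 10.5.1: "The primary, secondary, and additional efficacy endpoints will be analyzed using the ITT population".

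Adjudicated (composite) hemostatic efficacy is handled differently. Protocol Appendix B separates administrative from clinical reasons for a missing scan, gives patient deterioration as the clinical example, and rules: "Cases assessed as non-evaluable for clinical reasons will be imputed as having poor/none hemostatic efficacy". Protocol 10.5.3.1 gives death and unplanned surgery draining the hematoma as clinical examples, calls these cases treatment failures and keeps them in the denominator. SAP Table 3 counts nonevaluable cases of both kinds as poor/none in the primary analysis. SAP 5.5.7, which also sits under 5.5, counts nonevaluable hemostasis as poor/none whatever the reason.

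**The concern.** A patient who dies, deteriorates too far to be scanned, or has the hematoma drained is missing from this analysis because of how the bleed went. Deleting such patients changes the question from hemostasis on imaging in the ITT Set to expansion among patients well enough to be scanned. The two answers differ if the arms lose different numbers of patients this way, and can differ somewhat even if they do not.

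Protocol 3.3.2.1 regards volumetry as the most direct measure of hemostatic efficacy. In an open-label trial, the blinded core-laboratory reading is also the component least exposed to knowledge of treatment. Readers will therefore look to this endpoint when asking whether a composite result reflects less expansion.

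**Working it through.** **1. Does the text exclude these patients?** SAP 5.5.5 needs a measured volume change to assign a rating. Without a scan there is no change, SAP 5.5 forbids filling it in, and SAP 5.1 takes the percentage over nonmissing values. Naming the ITT Set does not prevent the loss, because a patient without a rating cannot enter the CMH table. The exclusion follows from the three sections together; the definition in 5.5.5 alone does not state it.

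**2. The plan's own figures.** None is given for this endpoint. The nearest are for the composite (SAP 3): 70% usual care, 80% andexanet, 450 per arm, about 90% power. The pooled standard error is sqrt(2 × 0.75 × 0.25 / 450) = 0.0289, so z = 0.10 / 0.0289 = 3.46. A two-look normal calculation at half and full information, with two-sided levels 0.0310 and 0.0277, gives 90.8% power. The plan's figure reproduces. The 70% and 80% are used below only as stand-ins, because the composite also counts NIHSS worsening and rescue therapy as failure.

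**3. Formula.** Let s be the success rate with clinically missing scans counted as failures, and m the share of the arm with such scans. Dropping them gives an observed rate of s / (1 − m). The documents give no m; 5% to 10% is assumed.

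Example, m = 10% usual care and 5% andexanet: 0.70 / 0.90 = 77.8% and 0.80 / 0.95 = 84.2%, a difference of 6.4 points.

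| m usual care | m andexanet | Observed usual care | Observed andexanet | Difference (points) | z, 450 randomized per arm |
|---|---|---|---|---|---|
| failure-coded | failure-coded | 70.0% | 80.0% | 10.0 | 3.46 |
| 5% | 5% | 73.7% | 84.2% | 10.5 | 3.77 |
| 10% | 10% | 77.8% | 88.9% | 11.1 | 4.24 |
| 10% | 5% | 77.8% | 84.2% | 6.4 | 2.37 |
| 5% | 10% | 73.7% | 88.9% | 15.2 | 5.60 |

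**4. Direction.** Equal loss enlarges the difference slightly. Setting 0.80 / (1 − mA) − 0.70 / (1 − mU) = 0.10, with mA and mU the losses on andexanet and usual care, and using 1 / (1 − m) ≈ 1 + m gives mA ≈ (0.70 / 0.80) mU, or 7/8 of mU. Under these rates the difference shrinks only if andexanet's loss is below roughly seven-eighths of usual care's. For example, 5% usual care and 4.5% andexanet gives 0.80 / 0.955 − 0.70 / 0.95 = 83.8% − 73.7% = 10.1 points, which is larger although andexanet lost fewer.

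**5. A case where the two analyses disagree outright.** Suppose scanned patients succeed at 80% in both arms. The nonmissing analysis shows no difference. With clinical loss of 8% on usual care and 3% on andexanet, failure-coding gives 0.80 × 0.92 = 73.6% against 0.80 × 0.97 = 77.6%, or 4 points in favor of andexanet. With the losses reversed it is 4 points against.

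**The case against.** The endpoint is meant to isolate imaging. Scoring an unscanned death as failure brings in non-imaging information, and the composite already counts these patients as failures. This stands as a reason to keep the nonmissing-only result, but not as a reason to leave the handling of outcome-related missingness to a blanket rule.

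Not every deteriorating patient is lost. Protocol 3.4 and 7.3 request extra imaging on deterioration, and SAP 6.1 lets the EAC accept an unscheduled scan as the 12-hour scan. For the composite, Appendix B counts growth above 35% on any scan between the end of initial treatment and 12 hours. All this is written for the adjudicated endpoint, and SAP 5.5.5 does not say whether such scans count here. The loss may therefore be smaller than feared, but the gap in the text is wider.

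A reader might infer that the SAP breaks a protocol rule. It does not: the poor/none rule is written for adjudicated hemostatic efficacy, and neither document extends it to the imaging-only endpoint. SAP 5.5.7 likewise uses the adjudicated status. It shows that 5.5 already admits exceptions to its blanket rule, no more.

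A reader might also infer that the exclusion understates the benefit of andexanet, or could hide early harm. The documents give no missing-scan rate by arm, and the table moves both ways. Harm would still show in the primary analysis and in the mortality summaries of SAP 5.7.2.5.

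**Conclusion.** The concern holds as a gap in SAP 5.5.5. Read with 5.5 and 5.1, the analysis drops ITT patients whose scans are missing for reasons tied to the outcome. Neither direction nor size can be stated. The range of about 6 to 15 points around a failure-coded 10 rests on two assumptions: composite rates standing in for unknown imaging-only rates, and clinical loss of 5% to 10% per arm.

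The consequence is limited. The endpoint lies outside the primary and secondary hierarchy of SAP 5.1.1, so the primary conclusion and type I error are untouched. It would be tempting to call it the main support for the composite, but the documents do not give it that role: Protocol 3.3.2.1 discusses volumetry as part of the primary endpoint. What is at stake is how far the imaging-only result can be used to interpret the primary one.

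**What to change.** Amend SAP 5.5.5 before unblinding:

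- Except this endpoint from the no-imputation rule in SAP 5.5.
- Rate a 12-hour scan that is missing or uninterpretable for clinical reasons, including death, deterioration or hematoma surgery, as poor/none.
- Treat administratively missing scans as missing. This matches the primary endpoint's sensitivity analysis 3 in SAP 5.3.3, which excludes administrative cases only.
- State that unscheduled scans accepted by the EAC count.
- Report the nonmissing-only analysis as a sensitivity analysis, with the number of missing scans by arm and reason.

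The cost is mostly wording, with one practical step. SAP 6.1 has the EAC classify the reason for a missing scan, but it also lets the algorithm rate clear cases immediately and words EAC referral for cases with volume change below 35% and NIHSS change below 7. A patient who already fails on NIHSS or rescue therapy and has no scan may never have a reason recorded. The SAP or Adjudication Charter should require the reason for those cases too. The downside is that for a few patients the endpoint is no longer purely a volume reading; a footnote can say so.
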